8.5 Stopping Rules

Subjects will be withdrawn from the study if they have a serious adverse reaction to any of the study drugs. Additionally, if patients are unable to complete the follow-up questionnaires they will be withdrawn. If patient's pain increases during the study period that is not tolerable without additional narcotic medication they will be withdrawn. Finally, we will withdraw patients from the study that no longer wish to participate.

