surgery and bolused with 10 mL of 0.5% ropivacaine. The pumps will be loaded with saline (single shot adductor canal group), or ropivacaine 0.2%, dispersed in either a continuous infusion (6 mL/hr) or pulsed intermittent bolus (8 mL every 2 hours). All groups will have a patient demand dose of 6 mL/hr for anterior knee pain. The medication for the adductor catheter will be dispersed to the anesthesia team by the research pharmacy. The anesthesia team will place the catheter under ultrasound guidance in the recovery room. They will adjust the delivery mode based on patient randomization. The anesthesia team will record the serial number of the pump at the time of placement.

Questionnaires will be sent electronically to the patient. Results will be collected daily for 14 days postoperatively, followed by weekly questionnaires until they discontinue narcotic medications. Additional questionnaires will be collected at 30 and 60 days postoperatively in order to record pain and KOOS Jr. scores. The questionnaires will be sent in the morning; if a patient fails to fill out the questionnaire by the afternoon, a member of the research team will contact the patient to obtain the data. The questionnaires will document numerical rating scale (NRS) pain scores, information on symptoms of nausea, vomiting, and constipation, and will inquire if the patient is still consuming narcotic medication.

Following discontinuation of the catheter the patient will remove and return the device to the supplier. The supplier will then provide the rate of on-demand usage to the research team by way of device serial number. This information will be stored in Redcap.

Subjects will be withdrawn prior to completion if they ask to be removed from the study. They may also be withdrawn from the study if they have a serious adverse reaction to one of the prescribed medications. Finally, subjects may be withdrawn at the discretion of the treating physician. If subjects are withdrawn early their last recorded pain score will be carried forward until study conclusion in order to perform intention to treat analysis. The study will continue to ascertain duration of narcotic use with weekly questionnaires, until the patient has stopped the medication.

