4.4 Early Withdrawal of Subjects

4.4.1 When and How to Withdraw Subjects

Subjects will be withdrawn from the study prior to completion if they ask to be removed from the study. They will also be withdrawn if they do not complete the protocol requirements or have a serious adverse reaction to one of the medications in the multi-modal regimen. Finally, subjects may be withdrawn from the study at the discretion of the treating physician.

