4.4.2 Data Collection and Follow-up for Withdrawn Subjects

If subjects are withdrawn from the study prior to completion we will collect the data prior to withdrawal. At the conclusion of the study we will note the number of subjects that were withdrawn from the study as well as the reasons for withdrawal.

5 Study Drug

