5.9.4 Return or Destruction of Study Drug

After the medication has been fully dispensed (postoperative day #4), patients will remove the adductor catheter and send the pump to Avanos for processing.

6 Study Procedures

6.1 Visit 1

At visit #1 patients will be screened for eligibility for inclusion in the study. If agreeable, an informed consent will be signed.

6.2 Visit 2

[figure not shown]
Patients will undergo standard preoperative clearance testing.

6.3 Visit 3

Patients will then proceed with the total knee replacement procedure. During the hospitalization we will record daily pain, nausea, vomiting, and constipation levels. Following the hospitalization these values will continue to be recorded daily utilizing an online questionnaire. If patients fail to complete the questionnaire then we will contact the patient via phone to record the daily value.

6.4 Visit 4

At 2 weeks the patients will return for a standard postoperative visit. The patient will then receive an online questionnaire weekly until they discontinue narcotic medication. They will receive additional surveys at 30 and 60 days following surgery.

7 Statistical Plan

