7.2 Statistical Methods

Descriptive and Inferential Statistics

Continuous variables will be summarized with the sample mean, median, standard deviation, minimum, 25th percentile, 75th percentile, and maximum. Categorical variables will be summarized with number and percentage of patients. All analysis will be performed on the basis of the intention-to-treat principle. Comparisons of endpoints between the three treatment arms will be made using a Wilcoxon rank sum test (continuous or ordinal endpoints) or Fisher's exact test (categorical endpoints). Missing data will be imputed using either the last observation carried forward method, a regression-based approach, or another method, depending on the extent of missing data. In order to adjust for the three pair-wise comparisons between treatment groups that will be made for each endpoint, we will utilize a Bonferroni correction for multiple testing, after which p-values of < 0.0167 will be considered as statistically significant. All statistical tests will be two-sided.

Primary Hypothesis:

We hypothesize that the intermittent bolus infusion cohort will report improved pain scores compared to continuous infusion catheters and placebo cohorts.

Secondary Hypothesis:

We hypothesize that the intermittent bolus cohort will require fewer doses of patient-administered medication and will use narcotic medication for a shorter duration when compared to the continuous infusion and placebo groups.

Interim Analysis

We will evaluate the first twenty patients. If 50% of the patients are withdrawn from the study for poor pain control or serious adverse reactions to the study medication, then we will close the study early.

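### Inability to complete questionnaires is a mandatory withdrawal reason with no threshold, so pain data that a phone call could recover are replaced by carried-forward scores, and post-withdrawal collection and interim classification are left unclear

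*Combined protocol and SAP*

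**What the plan says.** Two sections make failure to supply data a reason to leave the study. Section 8.5: "if patients are unable to complete the follow-up questionnaires they will be withdrawn". Section 4.4.1, more generally: "They will also be withdrawn if they do not complete the protocol requirements". Both are mandatory. Neither states how many misses are needed, over what period, or whether an attempt to reach the patient must fail first.

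Two other sections treat a missed questionnaire as recoverable. Section 3 says that if the form is not in by the afternoon, "a member of the research team will contact the patient to obtain the data". Section 6.3: "If patients fail to complete the questionnaire then we will contact the patient via phone to record the daily value".

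On what follows withdrawal, section 4.4.2 says "If subjects are withdrawn from the study prior to completion we will collect the data prior to withdrawal" and provides for nothing later. Section 3 says "If subjects are withdrawn early their last recorded pain score will be carried forward until study conclusion", and its next sentence adds "The study will continue to ascertain duration of narcotic use with weekly questionnaires, until the patient has stopped the medication". Section 8.4 unblinds patients who are withdrawn early. Section 7.3 defines the final analysis population as those who completed the study, while section 7.2 puts all analysis on an intention-to-treat basis.

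The interim rule in section 7.2 looks at the first twenty patients and counts withdrawals for two reasons only: "If 50% of the patients are withdrawn from the study for poor pain control or serious adverse reactions".

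**The concern.** Missing a questionnaire is a data problem; leaving the study is a change of status. Section 8.5 turns the first into the second. A patient who misses some daily scores but could still give later ones would have those later scores replaced by an old value. The arm would be revealed for an administrative reason, and the patient could fall outside the analysis set. The primary endpoint is the pain score, so the loss falls on the main comparison. It is also unlikely to be random, since pain, sedation or a complication are plausible causes of not answering, although the protocol says only that the patient is unable and gives no cause.

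Two further gaps follow. Section 8.2 has the team ask about adverse events whenever it is in contact with the patient, so if withdrawal ends the scheduled contacts, active detection of new events may end too. And where non-completion coincides with poor pain control or a serious adverse reaction, the interim count depends on which reason is written down.

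**Working it through.** The plan gives no calculated figure for this rule, so there is nothing to reproduce beyond the interim threshold: 0.50 × 20 = 10 patients.

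**1. The sections side by side**

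| Question | One place | Another place | Result |
|---|---|---|---|
| What happens after a missed questionnaire? | 3 and 6.3: contact the patient and record the value | 8.5 (and 4.4.1, broadly): withdraw | No statement of when the first gives way to the second |
| What is collected after withdrawal? | 4.4.2: data from before withdrawal | 3: duration of narcotic use still followed weekly | Not consistent; the section 3 route is a questionnaire, the instrument these patients could not complete |
| Pain after withdrawal | 3: last score carried forward | 7.2: imputation method chosen by extent of missing data | Later scores that could be obtained are imputed |
| Who is analysed? | 7.3: patients who completed the study | 7.2: intention to treat | Conflict for every withdrawn patient |
| Adverse events | 8.1 and 8.2: unresolved and ongoing serious events are followed | None of these sections says new events are sought after withdrawal | Silent |
| Interim count | 7.2: two reasons count | 8.5: several reasons can apply to one patient | No order of precedence |

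**2. How many patients could the rule reach?**

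The schedule in section 3 gives at least 14 daily questionnaires plus days 30 and 60, which makes 16. Let q be the chance that a questionnaire stays missing after the contact attempt. The documents give no value, so q is assumed, and misses are taken as independent. The share with at least one miss is 1 − (1 − q)^16.

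- q = 1%: 1 − 0.99^16 = 14.9%, or 12.5 of 84
- q = 2%: 1 − 0.98^16 = 27.6%, or 23.2 of 84
- q = 5%: 1 − 0.95^16 = 56.0%, or 47.0 of 84

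These are withdrawals only if a single miss meets the rule. At the same average rate, misses clustered within patients would lower the shares, as would values recorded by staff in hospital. The weekly questionnaires for patients still on narcotics are left out and would raise them.

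**3. What misclassification could do to the interim rule**

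Let p be the true rate of withdrawal for a counted reason, and m the share of those recorded instead as non-completion. Both are assumed. The chance of reaching the threshold is P(X ≥ 10), with X binomial (20, p(1 − m)).

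| p | m = 0 | m = 0.1 | m = 0.2 | m = 0.3 |
|---|---|---|---|---|
| 0.4 | 0.245 | 0.142 | 0.072 | 0.030 |
| 0.5 | 0.588 | 0.409 | 0.245 | 0.122 |
| 0.6 | 0.872 | 0.721 | 0.517 | 0.306 |

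So the recorded reason could matter if withdrawals were common. Nothing in the documents says that misclassification will occur or how often.

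**The case against.** The strongest reply is that the sections form a sequence: questionnaire, then staff contact, then withdrawal only of someone who cannot complete the questionnaires (plural) at all. The imputation plan in section 7.2, which depends on the extent of missing data, fits poorly with withdrawal after one miss, and section 4.4.1 does not name questionnaires. This is a fair reading and would bring the numbers well below those above. It does not supply the missing threshold, and it does not alter what follows once a patient is withdrawn.

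A reader might go further and infer that patients too ill to answer drop out of safety follow-up and escape the interim rule. The documents do not support that:

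- No section ends safety follow-up at withdrawal. Sections 8.1 and 8.2 keep known events under follow-up.
- Section 6.4 has a two-week visit for patients generally, which is when the adverse event reporting period in 8.1 ends. Section 8.6.1 adds an assessment for adverse reactions at that visit for the first twenty patients, who are the ones the interim rule covers. Patients 21 to 84 are told to call with concerns.
- A patient with a serious adverse reaction or intolerable pain also meets a separate withdrawal criterion in section 8.5 that the interim rule counts. Section 8.6.1 lists serious events that may end the study whatever the withdrawal reason.
- Data collection does not simply stop, because section 3 continues narcotic-use follow-up.

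What remains is silence: whether the two-week visit and the search for new events apply to withdrawn patients, and which reason prevails when several apply. Section 9.3 already requires missing data to be explained, and 4.4.2 and 7.3 record withdrawal reasons, so part of the remedy exists. None of these provisions keeps a non-completer in the study.

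**Conclusion.** The point holds as a defect in a stated rule. Applied as written, section 8.5 replaces recoverable pain scores with carried-forward values, unblinds the patient and, under 7.3, removes the patient from an analysis described as intention to treat. Sections 3 and 4.4.2 must be reconciled on follow-up after withdrawal. Loss of new adverse events and undercounting at the interim look are possible consequences of silence in the text; neither is stated.

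The number of patients affected is unknown. The range of 15% to 56% with at least one miss rests on assumed independent miss rates of 1% to 5% and on a one-miss reading of the rule. It does not measure lost safety events. The interim probabilities likewise rest on assumed rates. The change should be made because the rule gains nothing that the planned phone contact does not already provide, and removing it is cheap.

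**What to change.** - **8.5 and 4.4.1:** delete inability to complete questionnaires as a withdrawal reason in 8.5, and state in 4.4.1 that protocol requirements do not include it.
- **3 and 6.3:** treat a missed questionnaire as missing for that day, make the contact already planned, and send all later questionnaires. At that contact, record why it was missed and any adverse event.
- **4.4.2:** state, consistently with section 3, that pain, narcotic-use and adverse event collection continue to the end of their planned periods after withdrawal, unless the patient withdraws consent for follow-up.
- **7.2, interim analysis:** classify each withdrawal by its underlying cause, and use that cause for the count.
- **7.3:** reconcile the analysis population with the intention-to-treat statement in 7.2.

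The cost is wording in these sections and one reason-for-miss field in REDCap. The calls are already planned. The downside is continued contact attempts for a few patients.

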3.6 Primary Safety Endpoints

If patients report serious adverse side effects from a medication in the multi-modal regimen, or if they report uncontrolled pain, they will be withdrawn from the study and provided alternative medication per the treating surgeon's discretion.

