7.3 Subject Population(s) for Analysis

All patients who completed the study will be included in the final analysis. Additionally, we will note patient withdrawal rates as well as the reasons for patient withdrawal.

8 Safety and Adverse Events

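### Patients with intolerable or uncontrolled pain, the primary outcome, are withdrawn from the study, and the plan does not clearly say how their later scores are collected or analysed

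*Combined protocol and SAP*

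**What the plan says.** **Exit for pain.** Section 8.5 covers pain that increases to a level "that is not tolerable without additional narcotic medication they will be withdrawn". Section 3.6, after serious side effects of a medication, adds "or if they report uncontrolled pain, they will be withdrawn from the study". The interim rule in 7.2 confirms that such exits are intended, since early closure depends on this condition: "If 50% of the patients are withdrawn from the study for poor pain control or serious adverse reactions to the study medication". The withdrawal lists in Section 3 and 4.4.1 do not name pain, but both allow physician discretion.

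**Pain management on study.** Section 1.5 provides IV narcotic as a fallback in hospital and the standard opioid regimen at discharge. Section 3.1 lists as-needed oxycodone, tramadol and IV Dilaudid. Section 5.6 permits narcotic refills.

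**Data after exit.** Section 4.4.2: "If subjects are withdrawn from the study prior to completion we will collect the data prior to withdrawal". Section 3 says of withdrawn patients that "their last recorded pain score will be carried forward until study conclusion in order to perform intention to treat analysis", and continues weekly questionnaires to ascertain how long narcotics are used. Section 8.4 unblinds patients who are withdrawn early.

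**Analysis.** Section 7.2: "All analysis will be performed on the basis of the intention-to-treat principle". On gaps in the data, the same section says: "Missing data will be imputed using either the last observation carried forward method, a regression-based approach, or another method", with the choice depending on how much is missing. Section 7.3: "All patients who completed the study will be included in the final analysis".

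**The concern.** A patient who leaves because of pain leaves because of the endpoint. One arm receives saline, and the primary hypothesis in 7.2 is that intermittent bolus gives better pain scores than the other two arms. If that is right, exits for pain may differ by arm, and the patients without later scores are then not a random subset.

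The trigger is also unclear. Narcotics beyond the scheduled regimen are already allowed, so two clinicians could treat the same patient differently, one giving a refill on study and the other withdrawing the patient.

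What is at stake is the mean difference between cohorts (3.4) and the estimates that 7.1 intends to pass to the power analysis of a larger trial. A feasibility pilot is not excused on this point, because those estimates are one of its stated products.

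**Working it through.** No figure in the plan depends on this point, so there is none to reproduce. The check has three parts.

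**1. Which scores are provided for after exit**

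| Item | Schedule for patients on study | Provision after withdrawal |
|---|---|---|
| NRS pain | Daily to day 14, days 30 and 60, weekly while on narcotics | Carry-forward (Section 3); only earlier data collected (4.4.2) |
| Nausea, vomiting, constipation | Same questionnaires | None stated |
| KOOS Jr. | Days 30 and 60 | None stated |
| Narcotic duration | Weekly until stopped | Continues (Section 3) |

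The weekly form also carries NRS and symptom items (Sections 3 and 3.7). Some weekly scores may therefore be captured while narcotics continue, though the stated purpose is narcotic duration and the stated pain rule is still carry-forward.

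**2. How much of one patient's pain record is at risk**

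Fixed postoperative NRS scores: 14 + 2 = 16. Maximum loss for exit after the day-d score: (14 − d) + 2. The timing of weekly forms after exit is not given; days 7 and 14 are assumed.

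| Exit after day | Nothing captured | Weekly scores on days 7 and 14 | Weekly scores also stand in for days 30 and 60 |
|---|---|---|---|
| 2 | 14/16 (88%) | 12/16 (75%) | 10/16 (63%) |
| 4 | 12/16 (75%) | 10/16 (63%) | 8/16 (50%) |
| 7 | 9/16 (56%) | 8/16 (50%) | 6/16 (38%) |

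The last column needs narcotic use past day 60. Of the 4 catheter days (5.9.4), exit after day 2 loses days 3 and 4 in every column; exit after day 4 loses none.

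**3. What the choice of rule does to the estimate**

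Inputs: n = 28 per arm (3.2). Assumed: k patients withdrawn in an arm, whose mean score under carry-forward exceeds the completers' mean m by D points.

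Within one arm, carry-forward mean minus completers' mean:

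[(28 − k)m + k(m + D)]/28 − m = kD/28

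- k = 1: 2/28 = 0.07 (D = 2) to 5/28 = 0.18 (D = 5)
- k = 3: 6/28 = 0.21 to 15/28 = 0.54

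The endpoint is a difference between arms, so the quantity that matters is (k1·D1 − k2·D2)/28:

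- 3 versus 1 exits, same D: (6 − 2)/28 = 0.14 (D = 2) to (15 − 5)/28 = 0.36 (D = 5)
- equal exits and equal excess: 0

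**Illustration by simulation.** All inputs are assumed: 14 daily scores, NRS mean falling from 5 to 3, between-patient SD 1.5, within-patient SD 1.3, exit at the first score at or above a threshold, a shift of 1 point between two arms, and pain after exit following the same course as without exit.

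| Exit threshold | Exits, by arm | Full follow-up | Completers | Carry-forward |
|---|---|---|---|---|
| 8 | 27% vs 49% | 0.98 | 0.51 | 1.37 |
| 9 | 12% vs 27% | 0.98 | 0.66 | 1.29 |
| 10 | 4% vs 11% | 0.99 | 0.81 | 1.16 |

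Under these inputs the two rules err in opposite directions. With no true difference, all estimates were within about 0.015 of zero.

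**The case against.** The best defence is that the plan has a rule for withdrawn patients' pain. Section 3 carries the last score forward expressly for intention-to-treat, and narcotic duration is still followed. As-needed narcotics and refills may make exits rare, and this is a pilot without a power calculation. All of that is fair, and it limits the size of the point. It does not remove it: carry-forward substitutes an imputed value for scores that could be collected with surveys already scheduled.

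Scores after exit would also reflect the alternative medication given under 3.6, so using them is a choice of estimand. That choice does fit the stated intention-to-treat principle.

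Several stronger readings are tempting and are not supported:

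- **That 7.3 prescribes a completers-only analysis.** It says completers are included; it does not say others are excluded. The wording conflicts with Section 3 and 7.2, but exclusion is an inference.
- **That both postoperative KOOS Jr. scores are lost for every withdrawn patient.** Section 3.7 places KOOS Jr. on the 1-month and 2-month questionnaires of the same survey series, and weekly forms continue while narcotics do. The scores are not clearly provided for; certain loss is not shown.
- **That kD/28 is the bias in the treatment effect.** It is a gap within one arm, and it carries over to the contrast in full only if the other arm has no such exits.
- **That carry-forward always fixes a high score.** Questionnaires go out in the morning, so the last recorded score may precede the escalation that led to exit. A high score is likely but not documented.
- **That the interim rule shows many exits are expected.** Half of the first 20 is 10 patients, so 9 (45%) would not close the study; that is a stopping limit, not a forecast.

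**Conclusion.** The concern holds as a gap in the plan's wording with a possible effect on the primary estimate. Exit is tied to the primary outcome, its trigger is not defined against permitted narcotics, later scores are not clearly provided for, and the analysis sections allow more than one treatment of the same patient. Confidence in this is high.

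Confidence in a material effect is lower. The number of exits cannot be estimated from the documents. The 0.14 to 0.36 NRS points rest on assumed exits (3 versus 1) and an assumed excess (2 to 5 points), and the effect is zero if exits and excess are equal across arms. The figures concern means; no effect on the planned Wilcoxon rank sum test has been shown. The directions of bias in the simulation depend on its assumed inputs and should not be read as a prediction for this trial. The point merits an amendment because the remedy is cheap and the estimates are meant to feed a larger trial.

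**What to change.** - **3.6, 4.4 and 8.5:** intolerable pain leads to rescue analgesia and, if needed, stopping the catheter treatment, but not to leaving the study. Define *additional* narcotic against 3.1 and 5.6. The clinical threshold for stopping the catheter is for the investigators.
- **4.4.2:** continue the scheduled NRS, symptom, KOOS Jr. and narcotic-use surveys after treatment stops, unless consent is withdrawn.
- **8.4:** unblind only when care requires it, so that later self-reported scores are not routinely given after unblinding.
- **7.2, interim rule:** count patients whose study treatment is stopped for poor pain control or serious adverse reactions. Without this change, patients kept in follow-up would no longer count and the safety trigger would be weakened.
- **Section 3, 7.2 and 7.3:** analyse all patients as randomised, using collected scores, with carry-forward at most as a sensitivity analysis. Reword 7.3 to match.

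The cost is amendment wording across these sections, a few more of the surveys already scheduled, and a small survey burden for patients in severe pain. No rescue analgesia is restricted.
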